Any modifications to the protocol which may have an impact on the conduct of the study, potential benefit of the patient or may affect patient safety, including changes of study objectives, study design, sample sizes, study procedures, or significant administrative aspects will require a formal amendment to the protocol. Such amendment will be agreed upon by the Council of Oral Medicine and Periodontology Department and the Faculty of Dentistry, Cairo University.

26. Informed consent

Researcher will introduce the trial to patients and provide full explanation of its aim and benefits in layman language. Patients will then be able to have an informed discussion with the researcher. Researcher will obtain written consent from patients willing to participate in the trial. All consent forms will be translated into Arabic.

27. Confidentiality

All study-related information will be stored securely. All participant information will be stored in locked file cabinets in areas with limited access. All reports, data collection, process, and administrative forms will be identified by a coded ID [identification] number only to maintain participant confidentiality. All records that contain names or other personal identifiers will be stored separately from study records identified by code number. All local databases will be secured with password-protected access systems.

28. Declaration of interest

If there will be any conflict of interest it will be declared.

29. Access to data

The principal investigator and the supervisors will have access to the data sets. All data sets will be password protected. To ensure confidentiality, data dispersed to project team members will be blinded of any identifying participant information.

30. Post-trial care

All patients will be followed up for six months after the clinical trial is over.

31. Dissemination policy

- Study results will be published as partial fulfillment of the requirements for Doctorate's degree in Periodontology. - Topics suggested for presentation or publication will be circulated by the authors.

32. Informed consent

VI. Statement of originality

To the best of our knowledge, no randomized clinical trial has been published that involve comparing the clinical effect of surgical tube technique to hyaluronic acid gel injection in reconstruction of the tnterproximal papilla in patients with class II papillary defect.

VII. References

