VII. References							
	Evidence	based committee (Reviewers)					
Name		Signature	Date				
1.							
2.							
Research plan committee							
Name Signature Date							
1.		Signature	Date				
1.							
2.							

I. Administrative information:

1. Title

The clinical effect of surgical Tube technique versus Hyaluronic Acid gel injection in reconstruction of the interproximal papilla in patients with class II papillary defect. (Randomized clinical Trial).

2. Protocol Registration

3. Protocol version

First version.

4. Funding

Self-funding.

5. Roles and responsibilities

Main supervisor

[name] [name]

Associate Professor of Oral Medicine and Periodontology-Faculty of Dentistry-Cairo University.

[name]

Associate Professor of Oral Medicine and Periodontology-Faculty of Dentistry-Badr University.

- Initiation of the study.
- Generation of random sequence numbers and implementation of randomization.
- Supervision of surgical procedures.
- Revision of protocol and final thesis.

CO-supervisor

[name]

Lecturer of Oral Medicine and Periodontology-Faculty of Dentistry- Cairo University.

- Revision of final thesis.
- Supervision of surgical procedures.
- Recording clinical outcomes at baseline and different observation periods.

Main investigator

[name]

• Recruitment and allocation of patients.

- Preparation and follow-up of patients.
- Surgical treatment of patients.
- Preparation of protocol and thesis.

Trial responsibility:

Department of Oral Medicine and Periodontology, Faculty of Dentistry, Cairo University

Committees:

- Research plan committee
- Oral Medicine and Periodontology department council
- Evidence based dentistry committee
- Ethics committee
- Faculty Council

II. Introduction:

A. Background and rationale:

6. Research question:

In papilla class II defect will tube technique correct the papillary loss to fulfill complete gain in papillary height and embrasure fill compared to Hyaluronic acid injection?

The full occupation of the interdental papilla at the entire embrasure space apical to the interdental contact point/area., especially anteriorly, has been one of the most important aspects in increasing public demands for esthetics. Added to the esthetically unaccepted black triangle, loss of interdental papilla results in food impaction and plaque accumulation. Thus, negatively affects the integrity of the periodontal tissue health (*Burke etal 1994*).

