 - Healthy patients free of any medical condition.

Exclusion criteria:

- Patients with medical conditions that may affect periodontal healing or regeneration.
- Patients with a history of allergic reactions, pregnant or breastfeeding females,
 smokers and alcoholics
- Patients with current or previous drugs intake that may predispose to gingival enlargement.
- Patients under orthodontic treatment or had orthodontic treatment in the past six months.
- Carious teeth, proximal restorations or fixed prosthesis.
- Patients with a history of traumatic oral hygiene measures or periodontal surgeries over the last six months at the area of interest or having any scar tissue.
- Poor oral hygiene patients.

11. Interventions

11a-General operative procedure

- The patients who fulfil the inclusion criteria will be enrolled.
- The nature of the study will be explained to each patient as well as the importance of compliance with pre- and post-operative instructions and follow-up visits.
- Each patient will be asked to sign an informed consent (appendix 1)
- After enrolment, periodontal examination and full periodontal charts will be recorded for each patient including Papilla Class I1, CP-BC plaque Index (*Leary et al., 1967*), gingival bleeding Index (*Ainamo & Bay, 1975*), probing depth (PD), clinical attachment level (CAL) and gingival recession.

Radiographic Evaluation

Standardized digital periapical radiographs will be obtained preoperatively and at follow-up using the long cone paralleling technique. All radiographs will be obtained using the same equipment, film exposure and development conditions.

Pre-surgical therapy

- All patient will receive strict oral hygiene instructions full mouth supra and sub-gingival debridement using hand instruments and ultrasonic scalers under local anesthesia.
- Four to six weeks following pre-surgical therapy, a periodontal re-evaluation will be performed to confirm the suitability of the chosen sites for this periodontal surgical study.
- The clinical and radiographic parameters will be recorded at baseline

The patients will be randomly assigned into two groups: A total of 36 sites (18 site per group)

Group A (Intervention): Patients will receive Tube technique.

Group B (Control): Patients will receive Hyaluronic acid.

Surgical Procedures

Group A (Intervention): Patients will receive Tube technique (Hooshang et al. 2020).

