- 8) The size of the needle does not matter for this procedure; we use 4-0 silk with an FS2 cutting needle and a 4-0 chromic gut suture with a C-6 (FS-2) cutting needle.
- 9) Using the index finger and thumb the graft will be squeezed from both ends inward for at least 4 to 5 minutes to further stabilize the graft into position. Both patients are instructed to avoid

brushing or flossing the recipient as well as donor site. They are also asked to avoid hot, chewy, sticky foods. They were advised to ice the wound to reduce post-surgical swelling.

Group B (Control): Patients will receive Hyaluronic acid (HA) (0.1) mm (*Abdelraouf etal. 2019*) The product used in this trial is Restylane Lidocaine (Restylane-Lidocaine cross-linked Hyaluronic Acid Filler, Galderma S.A, Sweden). Restylane was the first FDA-approved HA filler in 2003. Restylane is a non-animal stabilised cross-linked HA filler with an HA concentration of 20 mg/ml. The longevity of Restylane filler in tissues is approximately 6 months. Restylane-Lidocaine (FDA approved in 2012) is a newer product of Restylane with 0.3% lidocaine incorporated into the syringe itself.

- -Stent will be performed and re evaluation
- -After 4 weeks, re-evaluation is performed, and the degree of papillary deficiency according to *Nordland and Tarnow* 1998 classification as well as plaque and gingival indices will be assessed for eligibility. Alginate impression is taken for the involved arch/arches for the construction of study casts and fabrication of customized stents. Only patients with deficient papilla sites fulfilling the inclusion criteria are recalled, scheduled for the 1st injection after 1 week and will sign the informed consent.

After 1 week 3 injection will be given at each papilla site

- -In the injection phase, 3 injections are given at each papilla site: at baseline, 3- and 6-weeks intervals. At the first injection visit, before attempting to inject, clinical measurement of the height of the black triangle is done by measuring the distance between the deficient papilla tip and contact area (PT-CP distance) to the nearest 0.5 mm (baseline). This will be done using a graduated periodontal probe and the fabricated customized stent for proper and standardized positioning of the probe at each measurement interval

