This power analysis used interdental papilla loss after six months as the primary outcome. Based upon the results of Awartani FA and Tatakis DN (2016), the mean and standard deviation (SD) for control group were 0.71 (0.74) mm2. The minimal clinically significant difference was 1 mm2according to expert opinion. Using alpha (α) level of (5%), β level of 0.8 (Power = 80%); the effect size for independent samples t-test (d) was 1.32 and the minimum estimated sample size was 10 sites per group. Sample size was increased to 12 sites per group to compensate for a drop-out rate of 20% after six months. Sample size calculation was performed using PS Power and Sample Size Calculations Version 3.

15. Recruitment strategy

- The main investigator will be responsible for recruitment of patients.
- Patients will be selected from the outpatient clinic of the Oral Medicine and Periodontology
 Department, Faculty of Dentistry Cairo University.
- Screening of patients will continue until the target sample is achieved.
- Identifying and recruiting potential subjects will be achieved through patient database.
- 1. One year.
- 2. Candidate self-funding

B) Assignment of interventions

16. Allocation

16a. Randomization

The patients will be randomly allocated to either the intervention group or the control group using computer generated random numbers that will be performed by the supervisor. The patients will be allocated in a ratio of 1:1.

16b. Allocation concealment mechanism

The two groups will be equally prepared for both surgical procedures. Then the decision of which group will receive Hyaluronic acid injection and which will Tube Technique will be taken according to the randomized numbers placed in opaque sealed envelopes. The number will be picked by the supervisor.

16c. Implementation

The supervisor will be responsible for generation of allocation sequence as will as assign the patients to the 2 intervention groups. The main investigator will be responsible for patient enrollment.

17. Masking/blinding:

Due to the type of intervention only the outcome assessor and the statistician will be blinded. Single blinded:

- Blinding of the participants is not applicable.
- Blinding of the operator is not applicable.
- Outcome assessor (primary and secondary outcomes) and biostatistician will be blinded.

Key elements of Random Sequence Generation in protocol are:

- 1-Method of random sequence generation (computerized random number generator).

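### The co-supervisor both supervises the procedures and records the clinical outcomes, yet Section 17 says the outcome assessor is blinded

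*Protocol*

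**What the plan says.** Section 5 of the protocol (Roles and responsibilities) lists three duties for the co-supervisor: revising the thesis, "Supervision of surgical procedures" and "Recording clinical outcomes at baseline and different observation periods". The main supervisors also hold supervision of the procedures. Outcome recording appears under the co-supervisor only.

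Section 17 (Masking/blinding) says: "Outcome assessor (primary and secondary outcomes) and biostatistician will be blinded". It also says "Blinding of the participants is not applicable" and "Blinding of the operator is not applicable".

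Three other places bear on the point:

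- Section 16b speaks of two surgical procedures: "The two groups will be equally prepared for both surgical procedures".
- Section 11a, under pre-surgical therapy, says "The clinical and radiographic parameters will be recorded at baseline" and only then describes random assignment.
- The Group B text of Section 11 places a baseline probe reading at a treatment visit: "At the first injection visit, before attempting to inject, clinical measurement of the height of the black triangle is done".

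**The concern.** Masking of the assessor is the only masking the protocol claims at the point of outcome measurement. Section 11 mentions pre-loaded syringes for patient blinding, but no syringe can disguise an injection from a graft operation, and Section 17 concedes that participants are unmasked.

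If the person who records the readings has watched the treatment being given, that single safeguard is lost. Probe readings involve judgement: Section 11 has the distance from papilla tip to contact read to the nearest 0.5 mm. Gain in papillary height, one of the probe outcomes, is also the quantity named in the protocol's only stated null hypothesis (Section 7). A later report of blinded assessment for these outcomes would have no support in this protocol.

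**Working it through.** No model or power calculation applies. The check sets the sections side by side and counts the outcomes affected.

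**1. Who records?** Section 5 assigns the recording of clinical outcomes, at baseline and follow-up, to the co-supervisor. Sections 11, 12, 16 and 17 name no separate assessor.

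**2. Does that person know the arm?** The same role supervises procedures. Group A receives buccal and palatal incisions and a harvested connective tissue graft. Group B receives injections at baseline, 3 weeks and 6 weeks. There are two readings of the supervision duty:

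- *It covers both treatments.* Section 16b supports this, and so does Section 11, where Groups A and B both stand under the heading for surgical procedures. The arm is then known for every patient supervised.
- *It covers the tube technique only.* Every patient supervised is then known to be in Group A.

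Either way the recorder is unmasked for the patients supervised, and no text keeps the co-supervisor away from treatment sessions.

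**3. Does Section 17 allow for this?** No. It claims blinding of the assessor for primary and secondary outcomes without exception.

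**4. Which outcomes are reached?** From the Section 12 table of secondary outcomes:

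| Measured by | Outcomes | Count |
|---|---|---|
| UNC periodontal probe | papillary height, CAL, PD, gingival recession, gingival bleeding, plaque index | 6 |
| Periapical radiograph | CP-BC distance | 1 |
| Patient questionnaire | satisfaction | 1 |
| Total | 6 + 1 + 1 | 8 |

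The primary outcome is read from photographs in image software by a reader who is not named. It may be read masked, so it is left out of the count.

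**5. Baseline timing.** Section 11a lists baseline recording before assignment, and Section 16b places the allocation decision after both groups have been prepared. The Group B text puts a baseline reading at the first injection visit. Unless the envelope is still closed at that moment, whoever takes the reading learns the arm before the 3- and 6-month readings.

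**6. Patient satisfaction.** Section 12 has the patient answer on a 7-point scale, and Section 17 says participants are not blinded. The blinded-assessor statement is therefore too wide for this secondary outcome.

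**The case against.** The strongest reply is that the conflict is inferred. Section 5 never calls the co-supervisor the outcome assessor, and it may not list all staff: the biostatistician of Section 17 is missing from it too. A separate masked assessor could exist, with the co-supervisor only writing readings down. This is possible, but the protocol does not say so, and Section 5 would then need correcting. It does not reconcile the two sections as they stand.

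Second, supervision is shared with the main supervisors, and the protocol elsewhere calls the injection non-surgical. The co-supervisor might attend only some cases. That stands as a limit: it would lower the share of patients whose arm is known, but it would not restore masking.

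Third, the count of six includes gingival bleeding, scored on all teeth, and plaque index, which the eligibility criteria treat as a full-mouth score. Neither is specific to the treated papilla, and neither is among the secondary outcomes in the PICOTS summary. The count is correct from the Section 12 table, but the four site-level outcomes (papillary height, CAL, PD and recession) are the ones most exposed.

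Fourth, the points on baseline timing and patient satisfaction are secondary. The first is conditional on when the envelope is opened. The second would probably mislead few readers, since Section 17 itself says participants are unmasked. Both still merit a sentence in the text.

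Fifth, the main supervisors may not be able to cover every procedure; one is based at another university. This bears on the cost of the fix and not on the contradiction.

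**Conclusion.** The point holds: the protocol is wrong as written and should be corrected. If a separate masked assessor exists, Section 5 is wrong; if not, Section 17 is wrong.

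The reach is 6 of 8 secondary outcomes, with the four site-level probe readings of most concern. The size of any bias cannot be estimated from the document. The primary outcome is not shown to be compromised.

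The conclusion rests on two assumptions: that the person assigned to record clinical outcomes is the one who takes the readings, and that supervising a procedure reveals which treatment was given. The second is hard to dispute for these two treatments. The first is the ordinary reading of Section 5, and nothing in the protocol contradicts it.

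**What to change.** 1. **Section 5:** remove supervision of procedures from the co-supervisor's duties and leave it with the main supervisors.
2. **Sections 5 and 17:** state that the person recording the clinical outcomes takes no part in delivering, supervising or allocating either treatment.
3. **Section 11:** state that baseline clinical readings in both groups are taken before the envelope is opened, and bring the Group B sentence into line.
4. **Section 17:** exempt patient satisfaction from the blinded-assessor statement.
5. **Clarification only:** state that black triangle area is read by a masked person from photographs coded to hide the arm.

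If the recorder cannot be kept apart from treatment, withdraw the claim of blinded assessment for the clinically recorded outcomes instead.

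The cost is text edits to Sections 5, 11 and 17, plus a sentence for the photograph reading if item 5 is adopted. No new staff are needed provided the main supervisors can cover the procedures, a duty they already hold. The price is one fewer senior person supervising them.

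### Allocation is given to two different roles, and under either reading the person allocating is the unblinded enroller-operator or the person who made the list, so concealment is weaker than it need be

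*Protocol*

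**What the plan says.** Section 5 (Roles and responsibilities) lists among the main investigator's duties "Recruitment and allocation of patients" and "Surgical treatment of patients". The same section, under the main supervisor heading, which names two people, lists "Generation of random sequence numbers and implementation of randomization".

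Section 16b (Allocation concealment mechanism) says the treatment is decided "according to the randomized numbers placed in opaque sealed envelopes" and adds: "The number will be picked by the supervisor". Section 16c (Implementation) reads: "The supervisor will be responsible for generation of allocation sequence as will as assign the patients to the 2 intervention groups". It then limits the other role: "The main investigator will be responsible for patient enrollment". Section 17 (Masking/blinding) says: "Blinding of the operator is not applicable".

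All of this is current text in a protocol that calls itself the first version, so no amendment explains the difference.

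**The concern.** Two things are wrong. First, the protocol does not settle who allocates: section 5 names the main investigator for it, and section 16c names the supervisor. Second, aligning the two role lists would not be enough, because the section 16 arrangement has whoever generated the sequence also draw the envelope, with no rule that envelopes are taken in a fixed order.

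What is at stake is selection bias at entry. The protocol's background says the response to hyaluronic acid depends on gingival biotype, but biotype is not an eligibility criterion. Eligibility also leaves room for judgement about motivation, oral hygiene and the suitability of the site. If prognostically different papillae can be directed to one arm, the arms differ at baseline. Blinded outcome assessment, which section 17 provides for, does not correct that, and in a trial of this size the analysis has little means of repairing it.

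**Working it through.** The point is mainly textual. The two sections compare as follows.

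| Step | Section 5 | Sections 16 and 17 |
|---|---|---|
| Generate the sequence | Main supervisor | Supervisor (16a, 16c) |
| Enrol | Main investigator | Main investigator (16c) |
| Assign | Main investigator (allocation), but also main supervisor (implementing randomization) | Supervisor (16c), who picks the number (16b) |
| Treat | Main investigator | Operator not blinded (17) |
| Order in which envelopes are used | Not stated | Not stated |
| Who holds the envelopes | Not stated | Not stated |

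**Reading A, following the investigator's duties in section 5.** One unblinded person recruits, allocates and operates. Nothing says this person has the list, so the envelopes still hide the next assignment. What is lost is the separation of enrolment from assignment: the same person judges the patient suitable and handles the envelope.

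**Reading B, following sections 16b and 16c.** Enrolment and assignment are separated. But whoever generated the sequence also picks the number. An opaque envelope hides its contents from people who do not know them, which is no protection against the person who wrote the list if that person may choose among envelopes. A fixed order would remove the choice, and none is stated. Section 16 refers to a single supervisor without saying which of the two named in section 5 is meant, so it does not divide the tasks between them.

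**Timing.** Section 11 records baseline parameters before describing random assignment. The timeline in section 13 puts eligibility and consent at T0, a round of clinical measurements at T1 and allocation at T2. The intended order is therefore largely right. The Group B text in section 11 blurs it, because it places a four-week re-evaluation for eligibility and the signing of consent inside the description of one arm.

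**Size, as an assumed illustration only.** The protocol gives no figure for this risk. Inputs:
- SD = 0.74 mm² (section 14, control group)
- target difference = 1 mm² (section 14)
- n = 12 sites per group (section 14) or 18 sites per group (section 11); the protocol gives both
- assumed, with no source in the documents: k sites per arm are swapped, and the swapped sites differ by 1 SD

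Each arm's mean moves by (k/n) × SD in opposite directions, so the shift in the difference is 2 × (k/n) × SD.

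- k = 2, n = 12: 2 × (2/12) × 0.74 = 0.25 mm²
- k = 2, n = 18: 2 × (2/18) × 0.74 = 0.16 mm²
- k = 1, n = 12: 2 × (1/12) × 0.74 = 0.12 mm²
- k = 1, n = 18: 2 × (1/18) × 0.74 = 0.08 mm²
- k = 0: no shift

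**The case against.** The strongest reply is that the conflict is narrow. Section 5 itself gives the supervisor the implementation of randomization, so one word in the investigator's duty list is out of line with three sections written for the purpose. Read alone, section 16 names a recognised safeguard and keeps the enroller away from assignment. Picking the number may be loose wording for taking the next envelope. Missing sequential numbering is an omission rather than a misstatement, and the timeline already puts consent and eligibility before allocation.

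Much of this stands, and it limits the point. A reader might infer that the trial has no allocation concealment; the sealed, opaque envelopes and section 16c contradict that. A reader might also infer that whoever allocates can foresee the next assignment under either reading. That is not supported for the investigator, who in no section generates or holds the list.

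Two things survive. The protocol does name two roles for the same task. And sections 16b and 16c do not merely leave something out: followed as written, they have the list-maker draw the envelope. The order of use matters because of that combination.

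**Conclusion.** The point holds as a weakness in how allocation is assigned and concealed, to be corrected before enrolment. Section 5 and section 16c conflict over who allocates, and neither arrangement separates list knowledge, enrolment and assignment as well as the existing staff would allow.

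The protocol shows an avoidable risk of selection bias. It does not show that assignments could be foreseen by the investigator, or that bias has occurred. The size of the risk cannot be derived from the documents. A reader might take 0.25 mm², a quarter of the 1 mm² target, as its measure. That would be wrong: the number steered and the 1 SD difference are both assumed, and the group size is itself unsettled. At most, steering two sites per arm would correspond to 0.16 to 0.25 mm², depending on which group size applies.

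**What to change.** - **Section 5:** delete allocation from the main investigator's duties, leaving recruitment, so that it agrees with section 16c.
- **Sections 16a to 16c:** have one main supervisor generate the list and seal sequentially numbered opaque envelopes. Have the other, who neither holds the list nor enrols, open them strictly in number order. Replace the wording about picking the number accordingly.
- **Section 16b:** state that the envelope is opened only after consent, eligibility and baseline measurements are recorded, in line with the order in sections 11 and 13.
- **Section 11:** reconcile the Group B text on re-evaluation and consent with that order, so that neither arm has a screening or consent step after its assignment is known.

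The cost is rewording, numbering the envelopes and some coordination. The two main supervisors are at different universities, and the protocol does not show that both can attend. The opening can be done remotely, for example by telephone. No additional patients or visits are needed.
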